# 2.2. Study Rationale

Clinical information from a previous study (A-101-SEBK-201) suggests that A-101 Solution 40% and 32.5% may safely and effectively resolve SK lesions on the back. A second currently ongoing study (A-101-SEBK-202) is evaluating the safety and efficacy of A-101 Solution 40% and 32.5% to remove SK lesions on the trunk and extremities. The rationale for this study is to evaluate the safety and efficacy of 2 concentrations of A-101 Solution (*i.e.*, 40% and 32.5%) and it's matching A-101 Solution Vehicle when applied to SK target lesions on the face. This study is designed to provide data to provide an understanding of the safety and efficacy of A-101 Solution for the removal of SK lesions on the face.

# 3. STUDY OBJECTIVES

The main objective of this study is to evaluate the dose-response relationship of 2 concentrations of A-101 Solution and its matching A-101 Solution Vehicle when applied to SK target lesions on the face. A further objective is to evaluate the safety and efficacy of 2 concentrations of A-101 Solution and its matching A-101 Solution Vehicle when applied topically up to 2 times to SK target lesions on the face.

# 4. SELECTION AND DISPOSITION OF STUDY POPULATION

## 4.1. Number of Subjects

Approximately 108 subjects will be randomized in this study with approximately 36 subjects randomized in each of 3 treatment groups. Subjects will be enrolled at multiple US investigational centers and enrollment will be competitive.

# 4.2. Study Population Characteristics

Male and female subjects, 18 years of age or older, with a clinical diagnosis of SK and 1 clinically typical SK target lesion on the face, who meet all the inclusion criteria and none of the exclusion criteria, will be eligible to enroll in this study.

#### 4.3. Inclusion Criteria

In order to be eligible for the study, subjects must fulfill all of the following criteria:

- 1. Subject is at least 18 years of age
- 2. Subject has a Fitzpatrick skin type of 1-4
- 3. Subject has a clinical diagnosis of stable clinically typical seborrheic keratosis
- 4. Subject has 1 appropriate seborrheic keratosis target lesion, as defined below (Section 5.4), on the face:
  - Have a clinically typical appearance
  - Be treatment naïve
  - Have a PLA of  $\geq 2$  (Section 6.1.2)
  - Have a longest axis that is  $\geq$ 7mm and  $\leq$ 15mm (Section 5.4)
  - Have a longest dimension perpendicular to the longest axis that is ≥7mm and ≤15mm (Section 5.4)
  - Have a thickness that is  $\leq 2mm$
  - Be a discrete lesion
  - Be, when centered in the area outlined by the provided 3cm diameter circular template, the only seborrheic keratosis lesion present
  - Not be on the eyelids
  - Not be within 5mm of the orbital rim
  - Not be covered with hair which, in the investigator's opinion, would interfere with the study medication application or the study evaluations (NB: the study medication may bleach hair)
  - Not be in an intertriginous fold
  - Not be pedunculated.
- 5. If the subject is a woman of childbearing potential, she has a negative urine pregnancy test and agrees to use an approved effective method of birth control (Section 8) for the duration of the study
- 6. Subject is non-pregnant and non-lactating
- 7. Subject is in good general health and free of any known disease state or physical condition which, in the investigator's opinion, might impair evaluation of the target lesion or which exposes the subject to an unacceptable risk by study participation
- 8. Subject is willing and able to follow all study instructions and to attend all study visits
- 9. Subject is able to comprehend and willing to sign an Informed Consent Form (ICF).

## 4.4. Exclusion Criteria

Any subject who meets one or more of the following criteria will not be included in this study:

- 1. Subject has clinically atypical and/or rapidly growing seborrheic keratosis lesions
- 2. Subject has presence of multiple eruptive seborrheic keratosis lesions (Sign of Lesser-Trelat)
- 3. Subject has a current systemic malignancy
- 4. Subject has a history of keloid formation or hypertrophic scarring
- 5. Subject has used any of the following systemic therapies within the specified period prior to Visit 1:
  - Retinoids; 180 days
  - Glucocortico-steroids; 28 days
  - Anti-metabolites (*e.g.*, methotrexate); 28 days
- 6. Subject has used any of the following topical therapies within the specified period prior to Visit 1 on, or in a proximity to the target lesion, which in the investigator's opinion, interferes with the application of the study medication or the study assessments:
  - LASER, light (*e.g.*, intense pulsed light [IPL], photo-dynamic therapy [PDT]) or other energy based therapy; 180 days
  - Retinoids; 28 days
  - Liquid nitrogen, electrodesiccation, curettage, imiquimod, 5flurouracil, or ingenol mebutate; 60 days
  - Glucocortico-steroids or antibiotics; 14 days
- 7. Subject currently has or has had any of the following within the specified period prior to Visit 1 on, or in a proximity to the target lesion, which in the investigator's opinion, interferes with the application of the study medication or the study assessments :
  - A cutaneous malignancy; 180 days
  - Experienced a sunburn; 28 days
  - A pre-malignancy (*e.g.*, actinic keratosis); currently
  - Body art (e.g., tattoos, piercing, etc.); currently
  - Excessive tan; currently
- 8. Subject has a history of sensitivity to any of the ingredients in the study medications
- 9. Subject has any current skin disease (*e.g.*, psoriasis, atopic dermatitis, eczema, sun damage, etc.), or condition (*e.g.*, sunburn, excessive hair, open wounds) which, in the investigator's opinion, might put the subject at undue risk by study participation or interfere with the study conduct or evaluations

10. Subject has participated in an investigational drug trial in which administration of an investigational study medication occurred within 30 days prior to Visit 1.

# 4.5. **Previous and Concomitant Therapies**

## 4.5.1. **Previous therapies**

At Visit 1, the investigator or designee will question the subject to ensure they have not used any excluded therapies (Section 4.4).

## 4.5.2. Concomitant therapies

Concomitant therapies are any new or existing therapy received from Visit 1 until discharge from the study.

Concomitant therapies include drug (*e.g.*, prescription, over-the-counter [OTC]) and non-drug (*e.g.*, chiropractic, physical therapy, energy-based treatments) therapies. Subjects will refrain from receipt of any therapy in compliance with the inclusion/exclusion criteria. Subjects should refrain from changing the use of any concomitant therapies during the study.

All new or modified concomitant therapies used during the study must be recorded.

Any new or modified concomitant therapy must be considered to determine if it is related to an AE. An AE must be reported unless the therapy is modified for non-medical reasons (*e.g.*, health insurance purposes) or it is for prophylaxis (*e.g.*, vaccinations).

# 4.5.3. Prohibited therapies

During the course of this study, subjects are prohibited from using therapies listed in the exclusion criteria (Section 4.4). The investigator should notify the Aclaris Therapeutics, Inc. Medical Monitor (Section 7.2) immediately if any prohibited therapies are required to ensure subject safety.

Starting with Visit 2, subjects must:

- On study visit days, not apply any topical products (*e.g.*, moisturizers, makeup, sunscreens, etc.) to the target lesion within 12 hours prior to any study visit (Note: routine cleansing products are allowed)
- Not apply any topical products to the target lesion for at least 6 hours after any study medication application.

Starting 6 days prior to Visit 2, and for the remainder of the study, subjects must not use any peroxide containing products on her/his face or head.

## 4.6. Subject Discontinuation from the Study

Subjects will be informed that they are free to withdraw from the study at any time and for any reason.

The investigator may remove a subject from the study if, in the investigator's opinion, it is not in the best interest of the subject to continue the study. Examples of other reasons subjects may be discontinued from the study are a change in compliance with an inclusion or exclusion criterion, occurrence of AEs, occurrence of pregnancy or use of a prohibited therapy. Immediately (within 24 hours) notify the Aclaris Therapeutics, Inc. study monitor of discontinuation.

In case of premature discontinuation of study participation, efforts will be made to perform all final study day assessments. The date the subject is withdrawn from the study and the reason for discontinuation will be recorded on the subject's case report forms (CRFs). All withdrawn subjects with ongoing AEs will be followed as appropriate (Section 7.2.1).

The study may be discontinued at the discretion of Aclaris Therapeutics, Inc. Some examples of reasons for discontinuation are the occurrence of the following:

- Increased frequency, severity or duration of known AEs
- Medical, regulatory or ethical reasons affecting the continued performance of the study
- Difficulties in the recruitment of subjects.

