## Number of Subjects:

Approximately 108 subjects will be randomized in this study at multiple United States (US) investigational centers with a goal of 96 subjects completing the study. Each investigational center is expected to randomize approximately 36 subjects. Subject enrollment will be competitive.

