# 5.6. STUDY DURATION

The duration of study participation is anticipated to be a maximum of 124 days per subject. This includes the up to 14 day screening period, a visit for the required first study medication application, a visit 21 days later for an optional retreatment study medication application and an 84-day no treatment follow-up period. The final study visit (Visit 8) has a maximum allowable visit window of 4 days.

The total study duration is anticipated to be approximately 166 days from the first subject's first visit to the last subject's last visit.

The study end date is the date of the last subject's last visit.

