# 5.7. STUDY MEDICATIONS

#### 5.7.1. Study medication identity

The study medications are water-clear, colorless solutions that are indistinguishable in physical appearance. The study medications must be stored in a secure area with limited access under appropriately controlled and monitored storage conditions.

| Study Medication Information |  |                         |                           |  |  |
|------------------------------|--|-------------------------|---------------------------|--|--|
| Study medication
name     | A-101 Solution
40%  | A-101 Solution
32.5% | A-101 Solution
Vehicle |  |  |
| Manufacturer                 | Pharmaceutical Manufacturing and Research Services,
Horsham, PA, US   |                         |                           |  |  |
| A-101 concentration
(%)   | n 40 32.5 0   |                         |                           |  |  |
| Pharmaceutical Form          | Solution   |                         |                           |  |  |
| Storage Conditions           | 68°F to 77°F (20°C to 25°C) protected from light, excessive heat, open flame and combustibles, out of direct sunlight and in a well-ventilated, dry area |                         |                           |  |  |
| Dose regimen                 |  |                         |                           |  |  |
| Route                        | Topical  |                         |                           |  |  |
| Frequency                    | 1 application to the target lesion at Visit 2;
a potential retreatment application to the target lesion at Visit 4                                    |                         |                           |  |  |
| Duration of administration   | Lin to 2 applications to the target lesion   |                         |                           |  |  |

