## 5.7.8. Dose modification

Study medication applications will be performed at Visit 2, and if appropriate Visit 4, by the investigator or an investigational center staff member at the direction of the investigator. No study medication will be dispensed to the study subjects.

If any subject refuses to allow the initial study medication treatment or a retreatment application, the investigator must report the visit number, visit date and the reason for the refusal on the subject's Comments CRF page.

If the subject's refusal is associated with an AE, the investigator must report the event on the appropriate CRF (Section 7.2).

The subject must have the initial study medication application to the target lesion to remain in the study.

The subject does not need to be removed from the study based solely on her/his refusal to have a study medication retreatment application on the target lesion.

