## 6.2.4. Urine pregnancy tests

The investigator or designee will perform a urine pregnancy test for subjects who are WOCBP (Section 6.2.4) at Visit 1, at Visit 2 prior to randomization and at Visit 8. The urine pregnancy test kits used must have a minimum sensitivity of 25-mIU ß-HCG/milliliter (mL) of urine.

Subjects who are WOCBP must have a negative pregnancy test result at Visit 1 to continue in the study and at Visit 2 to be randomized.

If the result of any post-randomization urine pregnancy test is positive, the subject will be withdrawn from the study and the subject's pregnancy documented and followed (Section 8).

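### Section 4.6 permits removing already treated subjects from the whole study; after Visit 4 this stops no study treatment and only loses the Day 106 outcome

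*Combined protocol and SAP*

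**What the plan says.** Section 4.6 lets the investigator take a subject out of the study when continuing is not in the subject's interest, and then gives examples of other grounds: "Examples of other reasons subjects may be discontinued from the study are a change in compliance with an inclusion or exclusion criterion, occurrence of AEs", and also "occurrence of pregnancy or use of a prohibited therapy". The wording is permissive and applies at any time. It does not distinguish a subject who still has an application ahead from one who has had the last. On leaving, "efforts will be made to perform all final study day assessments"; nothing provides for further follow-up to Day 106.

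Treatment is short and early. Section 5.7.1 gives one application at Visit 2 and "a potential retreatment application to the target lesion at Visit 4". Section 5.6 describes "a visit 21 days later for an optional retreatment study medication application and an 84-day no treatment follow-up period".

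Under Section 9.1 the primary analysis is an ANCOVA of PLA change from baseline to Visit 8 in the PP population, that is, completers without a major violation. ITT with LOCF is secondary. Non-completers are not replaced (Section 4.8), and the Synopsis plans for 108 randomized "with a goal of 96 subjects completing the study".

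Two sections already keep a subject in the study without a second application. Section 5.7.8 says of refused retreatment: "The subject does not need to be removed from the study based solely on her/his refusal". Section 5.7.6 withholds retreatment, with no mention of removal, when a local skin reaction is grade 3 and worse than at Visit 3, or when the investigator judges the lesion unsuitable.

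**The concern.** Leaving study treatment and leaving the study are different events, and Section 4.6 treats them as one. In most of this design only the second has any effect: once Visit 4 has passed there is no medication left to stop, so removal ends observation before the primary time point.

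The main objective is dose-response. AEs are among the listed grounds, and Section 5.7.6 itself foresees subjects leaving a treatment group because of medication-related AEs. If such removals are more frequent in one arm, the missing Visit 8 values depend on treatment and possibly on outcome. Neither the completer analysis nor LOCF repairs that. Discretion left to each site can also make the loss inconsistent between sites.

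**Working it through.** **1. Timing.** Nominal days are from Section 5.1: Visit 2 on Day 1, Visit 4 on Day 22, Visit 8 on Day 106.

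- Last possible application to endpoint: 106 − 22 = 84 days.
- First application to endpoint: 106 − 1 = 105 days.
- Share of follow-up with no treatment left to stop: 84/105 = 80%.

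**2. What removal does, by time of leaving.** PLA is scheduled at Visits 1, 2, 4, 6, 7 and 8 only (Section 6.1.2). In every row the subject is a non-completer and leaves PP.

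| Removed | Study treatment prevented | ITT value at Visit 8 if no exit PLA is obtained |
|---|---|---|
| After Visit 2, before Visit 4 | Possible retreatment | No post-baseline PLA to carry forward |
| After Visit 4, before Visit 6 | None | Visit 4 PLA, taken before any retreatment |
| After Visit 6, before Visit 7 | None | Day 50 PLA |
| After Visit 7, before Visit 8 | None | Day 78 PLA |

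For a retreated subject in the second row, the carried-forward value does not reflect the second application at all. If an exit PLA is obtained, it dates from the day of leaving rather than from Day 106.

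**3. The plan's own power figure.** Inputs from Section 9.3: n = 32 per group, clear rates 0.325 and 0.031, two-sided alpha 0.05, stated power about 87%. With the pooled-variance normal approximation:

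power = Φ{[(p1 − p2) − 1.96·√(2p̄(1 − p̄)/n)] / √(p1(1 − p1)/n + p2(1 − p2)/n)}

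Here p̄ = (0.325 + 0.031)/2 = 0.178, so power = Φ{(0.294 − 0.187)/0.0883} = 0.886. Exact enumeration of Fisher's test gives 0.852. The stated figure is reproduced. With all 36 per group assessed at Visit 8, power would be 0.921 (Fisher 0.908). The planned loss is already allowed for, so the issue is selection more than power.

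**4. Outer bound from the planned loss.**

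- Planned non-completers: 108 − 96 = 12; 12/108 = 11.1%, or 4 of 36 per group.
- Clear among 32 completers at the plan's rate: 0.325 × 32 = 10.4.
- Rate over 36 randomized if none of the 4 is clear: 10.4/36 = 0.289.
- Rate if all 4 are clear: 14.4/36 = 0.400.

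**5. The same question from the other side.** Assume a true clear rate of 0.325 in 36 subjects (11.7 clear) and, as an assumption only, 4 removals.

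- All 4 would have been clear: (11.7 − 4)/32 = 0.241.
- None would have been clear: 11.7/32 = 0.366.

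Steps 4 and 5 show how far four missing outcomes in an arm can move its rate. They do not estimate how many losses Section 4.6 would cause.

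**The case against.** Much can be said for the plan, and several stronger readings fail.

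- **Removal is permitted, not required.** A reader might infer that sites must discharge such subjects. Section 4.6 gives examples and leaves the decision open, and Section 4.5.3 asks for notice to the Medical Monitor, not removal, when a prohibited therapy is needed for safety.
- **The most obvious dose-related reason is partly covered.** Section 5.7.6 already handles a worsened grade 3 local reaction by withholding retreatment. Under Section 7.1.1, worsening of a target-lesion assessment is an AE only if medication is interrupted or stopped or therapy is needed. One cannot conclude that losses will be higher on active solution.
- **Sunburn, a tan or a topical antibiotic.** It is tempting to say that any of these near the lesion could end participation. Items 6 and 7 of Section 4.4 count only where the investigator thinks they interfere with application or assessment, and the check of continuing eligibility appears in the Visit 2 and 3 procedures but not in those for Visits 4 to 8.
- **Pregnancy.** Section 6.2.4 says "the subject will be withdrawn from the study and the subject's pregnancy documented and followed" after a positive post-randomization test, but the only scheduled one is at Visit 8, so that section costs almost no outcome data.
- **Size.** The 12 non-completers should not be attributed to Section 4.6. They are from all causes, and because Section 9.3 defines completion as for PP, they may include violators who do have Visit 8 data.
- **LOCF.** Carried-forward values need not be early; removals after Visit 6 or 7 use Day 50 or Day 78. The documents do not support a general claim that they come from a healing site.
- **Limited benefit to PP.** A subject retained after a prohibited therapy may still be excluded as a major violator.

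These points limit the size. They do not remove the gap: exit assessments are best effort and not tied to Day 106, and a subject removed for an AE without any major violation would otherwise have been a PP completer.

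**Conclusion.** The point holds as a design weakness, not an error of arithmetic. Section 4.6 allows removal from observation where, after Visit 4, no study treatment remains to be stopped, and it does not carry over the distinction already made in Sections 5.7.6 and 5.7.8. Between Visits 2 and 4 removal can also prevent a retreatment, so the statement that only the outcome is lost applies after Visit 4.

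The harm depends on how often sites use the discretion and whether AE-related removals differ by arm. The documents give neither figure. The 0.29 to 0.40 range rests on the plan's rate of 0.325 among 32 completers and on all 4 non-completers per group lacking a Visit 8 outcome; it is an illustrative limit, not an expected bias. The mandatory discharge of unblinded subjects (Section 5.10.2) is a separate rule and is not part of this point. Rating: a cheap improvement.

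**What to change.** Amend Section 4.6 to separate stopping study medication from stopping data collection. State that treated subjects who still consent, and for whom attendance is safe, are assessed at the scheduled visits through Visit 8 whichever Section 4.6 reason applies, with the event or deviation recorded and PP status decided as now.

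Reconcile 4.6 with 5.7.8 and 5.7.6. The latter ends retreatment for everyone when 3 or more subjects in a group discontinue from the study for related AEs. Because that trigger counts study discontinuations, the sponsor must say what it counts once such subjects may stay under observation. Decisions on study medication and on pregnancy management remain with the sponsor, and Section 6.2.4 needs no change for this purpose.

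The cost is a short amendment, with no visits or procedures beyond those scheduled. The downside is that some Visit 8 values will follow a prohibited therapy and must be flagged.

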# 4.7. Subject Number (SN)

The investigator will assign a unique four-digit subject number (SN) to each subject at Visit 1.

The SN format will be NN-NN where the first two digits are the investigational center site number (using leading zeroes as appropriate). The final two digits must be assigned in ascending numerical order, without omitting or repeating any number, starting with 01 at each investigational center. For example, the SN for the second subject that signs an informed consent at site number 01 would be 01-02.

The subject will be identified using the SN in all study documentation for the duration of the study.

#### 4.8. **Replacement Subjects**

Subject enrollment will continue until approximately 108 subjects have been randomized. Subjects who are randomized and do not complete the study will not be replaced.

# 5. INVESTIGATIONAL PLAN

## 5.1. Study Design

This is a randomized, double-blind, vehicle-controlled, parallel group study of 2 concentrations of A-101 Solution (*i.e.*, 40% and 32.5%) and its matching A-101 Solution Vehicle in subjects with SK. Eligible subjects will have 1 appropriate SK target lesion on the face.

The study will be conducted at multiple US study centers. The study visit schedule is:

- Visit 1 (Day -13 to 0) enrollment; start screening period
- Visit 2 (Day 1) randomization; study medication application
- Visit 3 (Day 8) no treatment follow-up
- Visit 4 (Day 22) follow-up visit where target lesions that meet the retreatment criteria will receive a second study medication application
- Visit 5 (Day 29) no treatment follow-up
- Visit 6 (Day 50) no treatment follow-up
- Visit 7 (Day 78) no treatment follow-up
- Visit 8 (Day 106) no treatment follow-up; end of study.

At Visit 1, the investigator will identify 1 SK target lesion on the face for treatment for each subject. Subjects may have more than 1 SK lesion, but only the target lesion will be evaluated and treated. The investigator will also collect blood samples for clinical laboratory safety tests to determine the subject's eligibility for randomization.

At Visit 2, the investigator will randomize eligible subjects and perform an initial study medication application.

At Visit 3, subjects will be seen for a no treatment follow-up.

At Visit 4, subjects will be seen for follow-up and any target lesion that meets the retreatment criteria (*e.g.*, PLA >0) will receive a retreatment study medication application.

At Visits 5 through 7, subjects will be seen for a no treatment follow-up.

At Visit 8, subjects will be seen for a no treatment follow-up and be discharged from the study.

